ID: JYLJ021

Clinical Research Program of Shanghai Ninth People's Hospital,
Shanghai Jiao Tong University School of Medicine

Establishment and Assessment of the HVPG using Biofluid Mechanics (HVPG_{BFM})

Study Protocol and Statistical Analysis Plan

Version: 1.3

Date: December 12th, 2018

Introduction

Portal hypertension (PH), an increased blood pressure of the portal vein and its branches, is one of the most severe syndromes caused by chronic liver diseases. Hepatic venous pressure gradient (HVPG) is currently the gold standard to detect portal hypertension.(1) HVPG value greater than 5 mmHg is defined as portal hypertension; HVPG value higher than 10 mmHg is considered as clinically significant portal hypertension (CSPH), which is highly associated with hepatocellular carcinoma and severe complications including gastroesophageal variceal haemorrhage, hepatic encephalopathy and ascites.(2)

However, the HVPG measurement is only available in few hospitals due to its invasiveness and technical difficulty.(3) In recent years, there are already several non-invasive portal hypertension assessment methods, including clinical examination, ultrasound, elastography, CT and MRI,(4) few of which, however, was proved to be accurate enough to replace the invasive HVPG measurement. Therefore, a less-invasive and accurate assessment method is needed and would be useful in the diagnosis and evaluation of portal hypertension.

Biofluid mechanics is the study of mechanisms of biological flows (liquid and gas) and their interrelationships with physiological and pathological processes by using fundamental principles of fluid mechanics.(5) Fortunately, recent advances in biofluid mechanics and image-based modelling make it possible for cardiologists to calculate fractional flow reserve, which is the gold standard assessment of the haemodynamic significance of coronary stenoses.(6) Moreover, biofluid mechanics may offer a new method for physicians to make an accurate assessment of HVPG noninvasively. The aim of the present study is to establish and validate the HVPG using biofluid mechanics (HVPG_{BFM}) model.

Methods and analysis

Study design overview

This study is a prospective, non-controlled, multicentre trial in patients with cirrhosis or portal hypertension.

Study population

Consecutive patients scheduled for HVPG measurement for clinical indications at Shanghai Ninth People's Hospital, Renji Hospital and Xinhua Hospital Affiliated to Shanghai Jiao Tong University School of Medicine are screened daily for study eligibility. Recruitment began on March 20th, 2018 and will continue until 200 participants have been recruited.

Inclusion criteria:

- Be at least 18 years of age.
- Patients with cirrhosis or portal hypertension, scheduled for HVPG measurement.

Exclusion criteria:

- Female patients who are pregnant or nursing.
- Patients who are medically unstable, terminally or seriously ill, or patients whose clinical course is unpredictable.
- Patients with clinically unstable cardiac disease, for example, congenital heart defect,

arrhythmia, uncontrolled heart failure (NYHA Class IV).

- Patients with respiratory distress syndrome or clinically unstable pulmonary disease, for example, pulmonary hypertension, pulmonary emboli, pulmonary vasculitis, emphysema.
- Patients with severe coagulation disorders.
- Patients with unstable occlusive disease or thrombosis within the hepatic, portal, or mesenteric veins.
- Patients who are allergic to iodinated contrast.

Ethics and informed consent

The trial complies with the latest Declaration of Helsinki. Written informed consent form will be obtained from patients or patients' legal guardian or patients' next of kin before the study begins. All participants can quit the study at any time without penalty or impact on the treatment. The study protocol, statistical analysis plan, informed consent form and case report form have already been approved by Scientific Research Projects Approval Determination of Independent Ethics Committee of Shanghai Ninth People's Hospital Affiliated to Shanghai Jiao Tong University School of Medicine. (Approval Number: 2017-430-T326)

Objectives

The primary objective of this study is to determine the numeric correlation between HVPG_{BFM} and HVPG. The secondary objective is to determine the diagnostic accuracy of HVPG_{BFM} for the diagnostics of PH and CSPH. The gold standard for the diagnosis will be the HVPG measurement.

Procedure of the study

Consecutive patients are randomly assigned 1:1 to either the original cohort or the validation cohort. Randomization is based on the computer-generated random digits table. This study consists of two independent and consecutive stages:

1. Establishment and improvement of the HVPG_{BFM} model: For 100 patients in the original cohort, biofluid mechanics specialists will use each patient's computed tomography, blood tests, Doppler ultrasound and HVPG results to adjust the parameters of the HVPG_{BFM} model in order to make each patient's HVPG_{BFM} and HVPG values match well.
2. Assessment of the HVPG_{BFM} model: For 100 patients in the validation cohort, biofluid mechanics specialists will use each patient's computed tomography, blood tests and Doppler ultrasound results to calculate each patient's HVPG_{BFM} according to the HVPG_{BFM} model established previously. Biofluid mechanics specialists will make no changes to the HVPG_{BFM} model and will have no access to patients' HVPG results in this cohort. Finally, the researchers will compare each patient's HVPG_{BFM} and HVPG value and make an assessment of the HVPG_{BFM} model.

Each patient's HVPG measurement will be performed after finishing computed tomography, blood tests and Doppler ultrasound. These results and other clinical data will be inaccessible to professionals for HVPG measurements in order to prevent certain biases. Each patient's computed tomography, blood tests, Doppler ultrasound and HVPG measurement will be performed within 30 days and treatments that may affect HVPG value will be avoided during this period.

The study design and procedure are shown in Figure 1.

[figure not shown]

Figure 1 Study design and procedure.

Examination

Computed Tomography

Each patient will undergo an abdominal contrast-enhanced computed tomography (CT) by multi-detector row CT scanners according to the protocol.(7, 8) The following parameters will be used: voltage, 120 kVp; current, automatic; collimation, 1.24-1.25 mm; Slice thickness, 0.625-2.5 mm; Slice interval, 1.0-2.0 mm; Matrix size, 512 × 512; rotation time, 0.5 s. A nonionic iodinated contrast agent (600 mg of iodine per kilogram of body weight, 300-370 mg

of iodine per ml, 3-5 ml per second) will be injected. Portal venous phase imaging will be performed 60-70 seconds after the beginning of intravenous contrast injection.

Blood tests

Each patient's blood samples will be collected from the cubital vein for blood viscosity test and density measurement. The blood viscosity test will be done by a ZL9100C blood rheology analyser (Zhongchi, China). The blood density will be done by weighing one millilitre of blood: one millilitre of blood will be pipetted by a Thermo Scientific™ Finnypipette™ F1 Pipettor onto a YP-B2002 electronic balance (Guangzheng, China) for weight measurement. The blood density measurements will be repeated at least three times and then be averaged.

Doppler Ultrasound

Each patient will undergo an abdominal Doppler ultrasound scan to measure the inner diameters and the maximum blood flow velocity of the inferior vena cava, the hepatic veins, the portal vein and its main branches after an overnight fast. The 12 measurement positions are: right branch of the portal vein, left branch of the portal vein, the portal vein, proximal part of the splenic vein, distal part of the splenic vein, the superior mesenteric vein, the inferior mesenteric vein, the right hepatic vein, the middle hepatic vein, the left hepatic vein, the suprahepatic inferior vena cava and the infrahepatic inferior vena cava. Each measurement will be done during deep inspiration breath-hold. All measurements will be repeated at least twice and then be averaged.

HVPG Measurement

HVPG will be measured by professionals according to established standards.(3) After finishing the computed tomography, blood tests and Doppler ultrasound, each patient will undergo an HVPG measurement after an overnight fast and local anaesthesia. The right internal jugular vein will be cannulated using a 6-French introducer (TERUMO Radifocus RS*A60K10SQ, Japan) under ultrasonographic guidance, then a 5.5-French compliant balloon-tipped catheter (Edwards Lifesciences Fogarty 12TLW805F35, USA) connected with a pressure monitoring set (Edwards Lifesciences TruWave PX260, USA) will be guided into the right or middle hepatic vein for the measurement of wedged hepatic venous pressure (WHVP) and free hepatic venous pressure (FHVP). WHVP will be measured when inflating the balloon to totally occlude the hepatic vein; FHVP will be measured when placing the catheter tip freely in the hepatic vein, at approximately 3 cm from its opening into the inferior vena cava. All measurements will be taken at least in duplicate and HVPG will be calculated from the difference between average WHVP and average FHVP. HVPG = WHVP - FHVP.

Computation

Geometry

Biofluid mechanics specialists will use IQQA-Liver software (version 2.0, EDDA Technology, Inc., USA) to convert the CT images from Digital Imaging and Communications in Medicine (DICOM) format files into stereolithography (STL) format files and create the simulation model of blood flow area in blood vessels accordingly. The model surface will then be meshed into triangle surface grids, each measuring from 0.2-1.0 mm, and the body meshes will be created accordingly. One case is shown in Figure 2.

[figure not shown]

Figure 2 An example of the simulation model of a portal venous system and its body meshes. (A) The simulation model of a portal venous system. (B) The body meshes of the simulation model.

Physical property

Biofluid mechanics specialists will use the blood viscosity of different shear forces (high, medium and low) to calculate the overall viscosity (Formula 1). Define a, b and c ($a + b + c = 1$) as weighting coefficients.

$$\text{Formula 1: overall viscosity} = a \times \text{viscosity}_{\text{high}} + b \times \text{viscosity}_{\text{medium}} + c \times \text{viscosity}_{\text{low}}$$

Boundary conditions

Biofluid mechanics specialists calculate the blood flow velocity at the boundaries of the main blood vessels according to the maximum blood flow velocity (measured by Doppler ultrasound), the inner diameter (obtained from the STL format files) and the principle of mass conservation (Formula 2). Define d ($0.7 < d < 1$) as the maximum blood flow velocity attenuation coefficient. One case is shown in Figure 3.

$$\text{Formula 2: average blood flow velocity} = d \times \text{blood flow velocity}_{\text{maximum}}$$

[figure not shown]

Figure 3 An example of the blood flow velocity of the portal vein and its branches.

The Navier-Stokes equations

The whole blood can be assumed to be an incompressible Newtonian fluid and blood flow can be modelled by the Navier-Stokes equations as follows:

$$\text{Formula 3: } \frac{\partial \rho}{\partial t} + \nabla \cdot (\rho \vec{v}) = S_m$$

$$\text{Formula 4: } \frac{\partial \rho}{\partial t} + \frac{\partial}{\partial x} (\rho v_x) + \frac{\partial}{\partial r} (\rho v_r) + \frac{\rho v_r}{r} = S_m$$

$$Formula 5: \frac{\partial}{\partial t}(\rho E) + \nabla \cdot (\vec{v}(\rho E + p)) = \nabla \cdot (k_{eff} \nabla T - \sum_j h_j \vec{J}_j + (\bar{\tau}_{eff} \cdot \vec{v})) + S_h$$

$$Formula 6: E = h - \frac{p}{\rho} + \frac{v^2}{2}$$

$$Formula 7: \frac{\partial}{\partial t}(\rho \vec{v}) + \nabla \cdot (\rho \vec{v} \vec{v}) = -\nabla p + \nabla \cdot (\bar{\tau}) + \rho \vec{g} + \vec{F}$$

$$Formula 8: \bar{\tau} = \mu \left[(\nabla \vec{v} + \nabla \vec{v}^T) - \frac{2}{3} \nabla \cdot \vec{v} I \right]$$

ρ : density; v : velocity; S_m : mass added to the continuous phase; x : axial coordinate; r : radial coordinate; v_x : axial velocity; v_r : radial velocity; h : enthalpy value; p : static pressure; $\bar{\tau}$: stress tensor; $\rho \vec{g}$: gravitational body force; \vec{F} : external body force; μ : molecular viscosity; I : unit tensor.

Establishment and improvement of the HVPG_{BFM} model in the original cohort

Empirical coefficients in initial: $a = 0.05$; $b = 0.05$; $c = 0.9$; $d = 1$. Calculate the overall viscosity and average blood flow velocity (formula 1 & 2) of one patient in the original cohort. Use the FLUENT software (version 6.3, ANSYS, Inc., USA) to solve the Navier-Stokes equations (formula 3-8) and get the simulated blood pressure on each volume grid. One case is shown in Figure 4. The simulated HVPG will be calculated from the difference between simulated portal pressure (PP_{BFM}) and simulated hepatic venous pressure (HVP_{BFM}), namely, HVPG_{BFM} = PP_{BFM} - HVP_{BFM}. Compare the simulated and measured HVPG. If they don't match well (their difference greater than 5%), then modify the value of a , b , c and d until they do. Record the value of a , b , c and d and the whole process for one patient is completed. Apply this process to each patient in the original cohort and record the value of a , b , c and d of each patient.

[figure not shown]

Figure 4 An example of the blood pressure of the portal vein and its branches.

Divide all patients into 9 groups according to their overall blood viscosity (high, medium and low) and their average blood flow velocity (high, medium and low): HighVis&HighVel, HighVis&MidVel, HighVis&lowVel, MidVis&HighVel, MidVis&MidVel, MidVis&lowVel, LowVis&HighVel, LowVis&MidVel, LowVis&lowVel. Calculate the statistical mean value of a , b , c and d of each group.

Calculation of the HVPG_{BFM} in the validation cohort

First, determine each patient's group according to the blood viscosity and blood flow velocity. Secondly, use the value of a , b , c and d of the specific group to calculate the geometry, physical property and the boundary conditions of each patient. Thirdly, use the FLUENT software to solve the Navier-Stokes equations and get the simulated blood pressure on each volume grid.

Finally, calculate the HVPG_{BFM}.

The summarized computation process is shown in Figure 5.

[figure not shown]

Figure 5 The process of the HVPGBFM computation

Sample size calculation

There will be 9 groups in the model. In order to obtain a precise model, no less than 10 samples for each group is needed in the original cohort, so the sample size estimated for the original cohort is 90 patients. It is anticipated that 10% of the patients recruited are likely to be excluded due to various reasons and therefore the target recruitment for the original cohort is 100 patients. The same number of patients will be recruited for the validation cohort. The total sample size is 200 patients.

Statistical Analysis Plan

Discrete variables will be summarized by frequencies and percentages and analysed by the χ^2

test. Continuous variables will be checked for normal distribution and summarized by either mean and standard deviations or median and interquartile range as appropriate. Comparison of continuous variables will be performed by using Student's t-test or ANOVA for normally distributed variables and the Mann-Whitney U test or Kruskal-Wallis test for non-normally distributed variables as appropriate.

The numeric correlation between HVPG_{BFM} and HVPG will be analysed by using Bland and Altman's limits of agreement analysis.(9) Bias is defined as the mean of the difference between HVPG_{BFM} and HVPG. Upper and lower limits of agreement are defined as average difference \pm 1.96 standard deviation of the difference. The numeric relationship between HVPG_{BFM} and HVPG will also be analysed with linear regression analysis, and to visualize the results, HVPG_{BFM} will be plotted against HVPG.

The diagnostic accuracy of HVPG_{BFM} for the diagnostics of PH (HVPG \geq 5 mmHg) and CSPH (HVPG \geq 10 mmHg) will be assessed by its sensitivity (Se), specificity (Sp), false-negative rate (FNR), false positive rate (FPR), positive predictive value (PPV), negative predictive value (NPV), diagnostic accuracy, Youden index (YI), likelihood ratio (LR+ and LR-) and Cohen's Kappa.

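### Does the unwritten sorting rule for the nine viscosity-by-velocity groups undermine the validation of HVPG_BFM?

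*Combined protocol and SAP*

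**What the plan says.** All places are in the combined protocol and SAP.

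- **Doppler Ultrasound** lists the sites: "The 12 measurement positions are: right branch of the portal vein" and eleven others.
- **Physical property** and **Boundary conditions** define the two quantities. Formula 1 makes overall viscosity a weighted sum of the high-, medium- and low-shear viscosities, with weights a, b and c. Formula 2 makes average velocity d times the Doppler maximum. The specialists "calculate the blood flow velocity at the boundaries of the main blood vessels", so several velocities exist per patient.
- **Establishment and improvement of the model in the original cohort** begins with "Empirical coefficients in initial" (0.05, 0.05, 0.9 and 1), then says "Calculate the overall viscosity and average blood flow velocity (formula 1 & 2) of one patient in the original cohort". The coefficients are tuned until simulated and measured HVPG differ by no more than 5%. The next instruction is "Apply this process to each patient in the original cohort and record the value of" the four coefficients per patient. Only then comes the sorting step, "Divide all patients into 9 groups according to their overall blood viscosity (high, medium and low) and their average blood flow velocity", followed by the mean coefficients of each group.
- **Calculation in the validation cohort** first determines each patient's "group according to the blood viscosity and blood flow velocity". It continues: "Secondly, use the value of a , b , c and d of the specific group".
- **Procedure of the study** makes the two stages consecutive, forbids changes to the model in stage 2 and withholds HVPG from the specialists there.
- **Sample size calculation** asks for at least 10 original-cohort patients in each of the nine groups.

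Figure 5, which summarises the computation, is not reproduced in the text available here and may settle some of the open points.

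**The concern.** The group is the only route by which the stage 1 calibration reaches a validation patient. It is part of the model under test, and three inputs to it are not written down: the Doppler site (or a summary over sites), the coefficient set used for sorting, and the cut rule. Because overall viscosity depends on a, b and c, and average velocity on d, it is fair to ask whether patients are sorted on starting, tuned or group-mean values.

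If the sorting cannot be repeated, neither can HVPG_BFM, and readers could not apply the validated tool. There is also a worry about tuned values. Since 0.7 < d < 1, tuning can change average velocity by up to 1/0.7 = 1.43-fold at the same Doppler maximum. Groups formed on tuned velocity would then have mean d values that partly reflect the sorting itself.

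**Working it through.** **1. The plan's own figures.** 9 groups × 10 = 90; 90/0.9 = 100 recruited; two cohorts give 200. All three reproduce.

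**2. Which coefficients can be used for sorting.**

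| Set | Original cohort | Validation cohort |
|---|---|---|
| Starting values | available | available |
| Patient-tuned values | available after tuning to HVPG | impossible, HVPG is withheld |
| Group means | known only after grouping | assigned only after grouping |

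Of the three sets, only the starting values work in both cohorts. With d = 1, Formula 2 gives average velocity = 1 × maximum, so velocity classes match those from the raw Doppler maximum. Viscosity becomes 0.05 × high + 0.05 × medium + 0.9 × low. The validation text, which sorts first and assigns coefficients second, agrees with this.

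**3. How much the excluded reading would matter.** Assume log-normal velocity with log-SD 0.2 to 0.4, and d unrelated to velocity.
- d uniform on 0.7 to 1: sorting on tuned velocity moves 30% to 16% of patients to another velocity third. Mean d, low against high, is 0.806 v 0.894 (ratio 1.11) at log-SD 0.2 and 0.827 v 0.873 (ratio 1.06) at 0.4. The true mean is 0.85 throughout.
- d uniform on 0.9 to 1, plausible because tuning starts at 1 and stops once the match is within 5%: 10% to 5% move, and the contrast is 1% or less.

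**4. Site.** For two bivariate-normal site velocities in cohorts of 90, the share changing velocity third is 51%, 42%, 35% and 26% at correlations 0.5, 0.7, 0.8 and 0.9. The documents give no correlation, so this is a range only.

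**5. Cut rule.** With 90 evaluable patients and 10 needed in each of nine groups, there is no slack, so the sample-size section presupposes roughly equal counts. Equal-width cuts under the step 3 velocity model put 6.5% to 11.2% of patients in the high class. That is 90 × 0.065 = 6 to 90 × 0.112 = 10 patients, where three groups of 10 need 30. Separate thirds on each axis are the natural reading, but they do not guarantee 10 per group. At n = 90 each third holds 30, so every group would have to hold exactly 10. If the axes are independent, that probability is (30!)^6 / (90! × (10!)^9) = 0.0021, or 0.2%. By simulation, the median smallest group is 7 at n = 90, and the chance that all nine groups reach 10 is about 8% at n = 100. At correlation 0.3 the chances are about 0.02% (n = 90) and 0.8% (n = 100).

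**6. Can the gap bias the validation?** The group depends on viscosity and velocity. The coefficients come from the original cohort. Validation HVPG enters neither, and the model is fixed before stage 2. Trying several cut rules in stage 1 would be ordinary model building, and its optimism would stay in the original cohort. In validation, the Bland-Altman bias and limits and the sensitivity and specificity describe whichever rule was carried forward. Misplaced patients add error to HVPG_BFM and so count against the model.

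**The case for a change.** The best counter-argument is that a rule nobody wrote down cannot be shown to have been fixed. The ban on model changes protects only what has been specified. Numeric cut-points could not be known in advance, but the method of choosing them could, and a few sentences would have supplied it. The validation section also drops the qualifiers overall and average, so the two cohorts' sorting variables are not worded alike.

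Much of this stands as a comment on description. No readable sentence names the site, the coefficient set or the cut rule, and a reader cannot rebuild the sorting from the text alone. It does not stand as a threat to the result. Both grouping variables are named and Formulas 1 and 2 define them. A rule that selects a to d is naturally part of the model that must not change, and the blinding covers the people applying it.

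Prescribing a particular scheme would not clearly be better. Velocity thirds nested within viscosity thirds would give exactly 10 per group at 90 patients, but HighVel would then mean different velocities in different viscosity classes. Sorting on one Doppler maximum would set aside the boundary velocities that the protocol derives from diameter and mass conservation. These are debatable preferences. The shortfall against 10 per group is a fair remark about the sample-size rationale, and it affects the precision of the group means rather than the honesty of the validation.

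**Conclusion.** The omission is real in the readable text, but it is missing detail that the analysts can fill sensibly, and no change to the plan follows. The order of steps and the withheld HVPG leave the starting coefficients as the only listed set usable in both cohorts. The sample-size reasoning points to roughly equal-sized classes, and the Doppler site is a stage 1 modelling choice.

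The effect is on reproducibility: 26% to 51% of patients could change velocity third with the site, under assumed correlations of 0.9 down to 0.5. It does not leak HVPG or inflate agreement or diagnostic accuracy, and no mmHg effect can be derived from the documents. The conclusion assumes that the sorting rule, like the rest of the model, is settled before validation patients are grouped, as the ban on model changes implies, and that the eventual report states the rule used. Figure 5 may already give part of it.

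### Ninety evaluable patients give an average of 10 per group, not a minimum of 10 in each of the nine groups, and the text has no rule for short or empty groups

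*Combined protocol and SAP*

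**What the plan says.** The section Sample size calculation begins "There will be 9 groups in the model", then says that "no less than 10 samples for each group is needed in the original cohort". From this requirement it draws its conclusion: "so the sample size estimated for the original cohort is 90 patients". An allowance of 10% for exclusions then gives 100 recruited. The validation cohort is set to the same number, so the total of 200 rests on this argument too.

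The groups are defined under Establishment and improvement of the HVPG_BFM model in the original cohort: "Divide all patients into 9 groups according to their overall blood viscosity" (three levels) and average blood flow velocity (three levels). The next step is "Calculate the statistical mean value of a , b , c and d of each group".

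Under Calculation of the HVPG_BFM in the validation cohort, each patient is placed in a group, and the specialists then "use the value of a , b , c and d of the specific group".

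Under Procedure of the study, "Consecutive patients are randomly assigned 1:1 to either the original cohort or the validation cohort". For the validation stage, "Biofluid mechanics specialists will make no changes to the HVPG_{BFM} model". Recruitment stops at a fixed total of 200.

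**The concern.** The plan states a minimum for every group but computes the size that gives that number on average. The 10% allowance covers exclusions and does nothing for uneven groups. The text does not fix the group sizes: randomisation is only between cohorts, no quota or stratification by viscosity or velocity is described, and no cut-offs for high, medium and low are given. Group counts are therefore a result of recruitment.

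This is the only justification of the sample size. The group means of a, b, c and d feed every validation prediction, and a small group gives less precise means. An empty group gives none, so a validation patient who falls in it could be computed only after a choice that the plan does not foresee. Such a choice would sit badly with the commitment to leave the model unchanged.

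**Working it through.** **Inputs from the documents.** Nine groups, a minimum of 10 in each, 90 evaluable, 10% exclusions, 100 recruited (Sample size calculation).

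**Inputs not in the documents (assumed).** The shares of patients in the nine groups. Three cases are used: equal shares of 1/9; sample thirds of each variable; and 25/50/25 sample splits of each variable. The last two are run with several correlations between viscosity and velocity.

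**1. The plan's own figure.** 9 × 10 = 90, and 90/(1 − 0.10) = 100. Both are reproduced.

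**2. Without any assumption.** 90/9 = 10 is the mean group size. If one group holds 11 or more, the other eight share at most 79, fewer than the 80 they need. So at 90 the minimum holds only when all nine groups hold exactly 10.

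**3. Equal shares.** At 90, the chance that all nine hold at least 10 is the multinomial probability of exactly 10 in each:

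90! / [(10!)⁹ × 9⁹⁰] = 1.8 × 10⁻⁷.

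At 100, with no exclusions at all, the exact multinomial sum is 0.0027. At 90 a given group falls below 10 with probability 0.45 (binomial, n = 90, p = 1/9), so 9 × 0.45 ≈ 4.1 groups are expected to be short.

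**4. Sample thirds, uncorrelated.** Each level holds 30 of 90, and the chance of exactly 10 in every group is

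(30!)⁶ / [90! × (10!)⁹] = 0.0021.

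**5. All cases.** Correlated cases are simulated from bivariate normal ranks, 40,000 runs each.

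| Assumed grouping | P(all nine ≥ 10), n = 90 | P(all nine ≥ 10), n = 100 | Expected smallest group, n = 90 | P(an empty group), n = 90 |
|---|---|---|---|---|
| Equal shares | 1.8 × 10⁻⁷ | 0.0027 | 5.6 | 0.02% |
| Thirds, correlation 0 | 0.0021 | about 0.08 | 7.0 | 0% |
| Thirds, correlation 0.3 | about 0.0001 | about 0.007 | 5.4 | under 0.1% |
| Thirds, correlation 0.5 | under 0.0001 | under 0.0001 | 3.4 | about 1.1% |
| 25/50/25, correlation 0 | impossible | impossible | 3.5 | 0.3% |
| 25/50/25, correlation 0.3 | impossible | impossible | 2.2 | about 6% |
| 25/50/25, correlation 0.5 | impossible | impossible | 1.0 | about 33% |

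The 25/50/25 entries are impossible because an end level of 22 to 25 patients cannot hold three groups of 10. With thirds and correlation 0.7, the expected smallest group is 1.4 and the chance of an empty group is about 20%.

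**6. Size needed to keep the minimum.** Under equal shares, the chance that all nine groups reach 10 first passes 80%, 90% and 95% at 151, 163 and 173 evaluable. The recruited number for 80% is 151/0.9 = 167.8, so 168. With sample thirds, 80% needs about 130, 177 and 280 evaluable for correlation 0, 0.3 and 0.5. If the cut-offs are fixed at population thirds instead, correlation 0.3 needs 194.

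**7. Effect on prediction.** Assume that the variance for a patient in a group of size n is s²(1 + 1/n), a form the documents do not give. Exactly 10 per group gives 1.1 s². Under equal shares at 90, averaging 1/n over the possible group sizes gives about 0.111, and √(1.111/1.1) ≈ 1.005. The overall prediction standard deviation rises by about 0.5%. Sample thirds with correlation up to 0.5 give less.

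**The case against.** The strongest reply is that little depends on the number. The plan sets no precision target for the group means, the agreement analysis needs no minimum group size, and the rise in overall prediction standard deviation is about half a percent or less. This stands, and it limits the weight of the point. It does not rescue the justification, which states a minimum for each group and draws 90 from it.

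A second reply is that the grouping method is left open. Cutting velocity into thirds within each viscosity third would put exactly 10 in every group at 90, and the text does not exclude this. But the text does not describe it, and common cut-offs are the more natural reading of the nine labels.

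Third, Figures 1 and 5 were not available for this review and could hold cut-offs or a fallback rule. The finding of no rule is therefore limited to the text. The confusion of average with minimum would remain unless a figure fixed the group sizes.

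Fourth, an empty group is likely only under strong correlation or uneven splits, for which the documents give no support. That is fair: short groups are the expected outcome, and an empty one is a contingency.

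A related gap also stands. Overall viscosity and average velocity depend on a to d (Formulas 1 and 2), and the text does not say which values are used to classify patients. A rule for short groups cannot be applied until that is settled.

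**Conclusion.** The concern holds. The arithmetic is correct, but 90 evaluable patients deliver an average of 10 per group and not the stated minimum. This needs no assumption beyond the absence, in the text, of any device that makes the groups equal. In every case examined without such a device, the chance of meeting the minimum at 90 is about 0.2% or less. At 100 with no exclusions it is at most about 8%. The expected smallest group at 90 ranges from 7.0 down to 1.0 across the cases, and those figures depend on group shares that the documents do not give.

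The point should be corrected. It concerns the justification and a missing rule, and it does not undermine the validation itself.

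**What to change.** Keep 100 per cohort. In Sample size calculation, drop the claim that 90 secures at least 10 in each group and replace it with wording such as:

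> About 90 evaluable patients give an average of about 10 per group. Group sizes are not fixed by design, and some groups are expected to hold fewer than 10.

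If an expected smallest group is quoted, name the assumed shares and correlation.

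Before any validation computation, state how patients are classified (cut-offs, and which coefficient values are used) and set one rule for short or empty groups. The choice of rule is the sponsor's. Pooling with the adjacent velocity level in the same viscosity level is one example.

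This costs wording and one rule, and no patients. The drawbacks are a less favourable stated figure, no stated reason why an average of 10 is enough, and less group-specific coefficients where groups are pooled.

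If the sponsor prefers to keep the minimum, there are two options:

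- **A larger original cohort.** Under equal shares, 168 recruited gives an 80% chance, which is 168 − 100 = 68 more patients. Most of the correlated or uneven cases need more; uncorrelated sample thirds need fewer. If the validation cohort is kept equal in size, the addition doubles to 136.
- **Nested cut-offs.** Velocity thirds within each viscosity third give exactly 10 per group at 90, but the velocity cut-offs then differ between viscosity levels.
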